#### **11.5.2 Effect of HIV Seek and Test Strategies and Impact of Substance Use on Clustered Transmission:**

First, initial analysis will assess process measures evaluating, for example, the % HIV infections in MSM and transgender women that are detected during AHI compared to our preliminary data from 2007-2008 and rates in historical controls [182], and the proportion of MSM and transgender women with AHI diagnosed by point-of-care vs. lab-based assays who are successfully linked to care.

Second, summary statistics on the inferred phylogenetic tree will be computed, including the number of clusters identified, the percentage of MSM and transgender women in the cluster, the number of infections in each cluster, and the maximum window periods for onward transmission within each cluster. To evaluate the impact of partner services we employ on finding transmission clusters, we will also compare the percentage of MSM and transgender women in the cluster to that percentage seen in the literature using other approaches, e.g., 49.4% in [162], 34% in [183]. McNemar's test will be conducted to evaluate the agreement between being in the clusters based on partner tracing and being in the clusters based on phylogeny.

Third, we will compare the sexual behaviors, and use of alcohol or drugs such as cocaine between MSM and transgender women clustered by phylogeny and MSM and transgender women not clustered by phylogeny (using 2 set of trees: MSM and transgender women with acute/recent infection with or without partners). Our analysis of the impact of substance use on clustered transmission will include all MSM and transgender women with acute/recent infection and their partners. For example, we anticipate that roughly 5% of index cases with AHI will use

cocaine and roughly 25% will have AUD based on a recent study of high risk MSM and transgender women in Lima [184]— this analysis will assess whether either cocaine use or AUD are enriched among men in transmission clusters. For outcomes measured at a single time point, we will use Chi-squared tests, Fisher's exact tests or Mann-Whitney U tests, as appropriate. For outcomes measured longitudinally, we will use the generalized estimating equation approach to account for correlations among repeated measures.

Fourth, baseline questionnaire data on substance use and sexual behavior will also be compared between MSM and transgender women with acute and recent HIV infections after stratifying on AUD. Both univariate comparison and multiple regression to explore risk factors that are associated with acute/recent infection will be conducted.

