## Test and Treat Early HIV among MSM and Transgender Women in Lima, Peru

be responsible for a considerable share of HIV-1 transmission, since a larger proportion of infected persons have acute or early-stage disease rather than late-stage disease [162]. Sexual behavior plays an important role in rates of infection, with high rates of partner change increasing the chances of contact with a person who has acute HIV-1 infection. In a recent comprehensive study conducted in Lilongwe, Malawi, in which both behavioral and biologic data were used, 38% of cases of HIV-1 were ascribed to sexual exposure to patients in the first 5 months of infection, even though there is a long-established epidemic in Malawi. The results of the Malawi study may be most relevant to the HIV-1 pandemic in sub-Saharan Africa. The importance of acute HIV-1 infection can also be seen in studies of phylogenetically related cases. In Montreal more than half the patients with newly diagnosed early HIV-1 infection are infected with viral variants that can be linked through phylogenetic studies, which suggests the presence of clusters of transmission, perhaps from patients with acute and early infection [162].

**Figure 3. Role of Acute and Early HIV-1 Infection in the Spread of HIV-1, According to Population Studies in Sub-Saharan Africa, the United States, and Europe (from [110]).**

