### **11.3 SAMPLE SIZE AND ACCRUAL**

Our goal is to enroll approximately 75-90 men with AHI and 75-90 with RHI in three years, with a target of enrolling 25-50 men with AHI and 25-50 men with RHI per year, or approximately 2-4 men in each group per month. We expect that another 50 men will be identified with acute or recent HIV-1 infection who will either not meet all inclusion requirements or who will not consent to enrollment in the study. Specimens for sequencing will be collected from all men.

Samples for sequencing will be obtained from all identified HIV+ partners of the 200 men with acute/recent infection (we anticipate that not all men will consent to partner tracing). Our initial sequencing efforts will focus on the 100 acutely infected men (75 enrolled plus 25 non-enrolled in immediate/deferred ART study) and their HIV+ partners (especially those with acute or recent HIV infection), testing a total of 400 samples. The first available sample will be sequenced with 454/pyrosequencing and analyzed as described below.

Semen HIV VL will be measured in samples from 60 (30 acute/30 recent) men in the immediate ART group and 60 (30 acute/30 recent) men in the deferred treatment group using established procedures in The University of Washington Virology Laboratory [177, 178]. We will seek separate funding to analyze additional samples, including rectal secretions.

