Next-generation deep sequencing using the 454/Pyrosequencing platform will be used to generate envelope gene sequences from each study participant using plasma from the first available time point following infection. Deep sequencing provides us with the opportunity to identify relatively low-frequency variants in each infection. This is important because we have found that in a significant fraction of the cases, divergent, low-frequency variants are often involved in transmission to a new host [181]. To provide context for the identification of linked transmissions, we will prepare two HIV-1 envelope gene sequence databases corresponding to the same genetic region as Lima. The first dataset will contain all available Peruvian HIV-1 sequences from the Los Alamos National Laboratory HIV Sequence Database (HIVDB) (<http://www.hiv.lanl.gov/content/sequence/HIV/mainpage.html>), as well as subtype B sequences from other countries in South America. This will enable us to determine the expected spread of genetic relationships from individuals without epidemiologic linkage. Second, a “linked” database of corresponding HIV-1 envelope gene sequences from 147 known transmission pairs [181] will be generated to enable us to determine the expected spread of genetic relationships from individuals with known epidemiologic linkage. HIV-1 linkage will be assigned by requiring the following: 1) pair derived HIV-1 env sequences from two or more individuals form monophyletic clusters (i.e., originating from the same terminal node) in maximum-likelihood phylogenetic trees that include all available sequences from unrelated individuals and 2) the pairwise genetic distances are required to be associated with a Bayesian posterior probability >50%. Pairs of sequences that meet these two requirements are tentatively classified as linked. In this manner, a phylogenetic tree containing clustered and unclustered sequences will be constructed for all acutely infected index cases and their HIV+ recent sexual contacts. These clusters are due to high-level transmission which occurs early after infection, before sequence divergence. (If funding allows or additional funding is available, specimens from men with recent infection and their partners will be sequenced and added to this analysis.)

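### Section 11.5.2 judges what partner services add to cluster finding by a descriptive comparison with published percentages, which cannot isolate it; a paired comparison of trees without and with traced partners would measure the added yield

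*Combined protocol and SAP*

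**What the plan says.** The second analysis in section 11.5.2 lists summary statistics on the phylogenetic tree and then gives one comparison a purpose of its own: "To evaluate the impact of partner services we employ on finding transmission clusters". For that purpose the plan will "compare the percentage of MSM and transgender women in the cluster to that percentage seen in the literature using other approaches, e.g., 49.4"% in one cited study, with 34% in a second. No adjustment, test, significance level or rule for choosing between the two figures is given. The next sentence plans a McNemar test, "conducted to evaluate the agreement between being in the clusters based on partner tracing" and by phylogeny.

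The third analysis in the same section mentions trees built two ways, "using 2 set of trees: MSM and transgender women with acute/recent infection with or without partners". It uses them only to compare behaviour and substance use between clustered and unclustered participants.

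Section 11.5.1 sets the linkage rule: envelope deep sequencing, a monophyletic cluster in the maximum-likelihood tree, and "the pairwise genetic distances are required to be associated with a Bayesian posterior probability >50"%. It says this approach has not been applied to clusters before. The tree it commits to holds acutely infected index cases and their HIV-positive recent contacts; recent infections are added only if money allows. Section 11.3 agrees: "Our initial sequencing efforts will focus on the 100 acutely infected men (75 enrolled plus 25 non-enrolled") and their HIV-positive partners. It also expects some men to decline partner tracing.

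**The concern.** A comparison meant to show what partner services add should differ from its comparator in partner services alone. Here several things differ together. The setting is Lima. The sampled share of the epidemic is this study's own. The linkage rule is new to cluster identification. The tree contains people included because they are contacts of index cases. The section also does not say whether those contacts count in the percentage.

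At stake is a statement in the final report that partner services did or did not help find clusters. On this comparison, that statement could go either way for reasons unrelated to tracing.

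**Working it through.** **Inputs from the documents.** Benchmarks 49.4% and 34% (11.5.2); 100 acute index men, of whom 75 enrolled (11.3). The plan gives no sample size, power or significance level for this comparison, so there is no planned figure to reproduce. All rates below other than the two benchmarks are assumptions.

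**1. Distance between the benchmarks.** 49.4 − 34 = 15.4 points.

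**2. What the gap contains.** Let r be the percentage of Lima index cases that would cluster without traced partners, g the gain from tracing, and b the benchmark. The observed gap is (r + g) − b = g + (r − b). The term r − b is unknown and has nothing to do with tracing. With g = 0 and r = 45%, the gap is 45 − 34 = +11 points against one study and 45 − 49.4 = −4.4 against the other. Any total between 34% and 49.4% gives opposite signs.

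**3. The same with a real gain.** Let c be the share of index men clustered without partners and p the share with a sequenced, linked traced partner, taken as independent. The share with partners is c + p(1 − c).
- c = 30%, p = 20%: 0.30 + 0.20 × 0.70 = 44%, a true gain of 14 points. The literature comparison shows +10 and −5.4.
- c = 30%, p = 10% to 40%: 37% to 58%, a true gain of 7 to 28 points.

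**4. Denominator.** Take the 44% case with 100 index men. Suppose 20 of them have one linked partner each and no other partner is sequenced. Counting index men only gives 44/100 = 44%. Counting everyone in the tree gives (44 + 20)/(100 + 20) = 53.3%, which is 19.3 points above 34% and 3.9 above 49.4%. Sequenced but unlinked partners would pull the second figure down. The same data can thus change sign against 49.4% through the denominator alone.

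**5. If someone attached a test.** The plan does not. As an illustration only, take an exact two-sided 5% binomial test with the benchmark treated as fixed and no effect of tracing:

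| Underlying rate | Tested against | Verdict | n = 100 | n = 75 |
|---|---|---|---|---|
| 49.4% | 34% | higher | 0.88 | 0.72 |
| 34% | 49.4% | lower | 0.88 | 0.77 |
| 45% | 34% | higher | 0.62 | 0.43 |

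Conversely, a real rise from 34% to 49.4% would show no difference from the 49.4% benchmark about 95% of the time. At n = 100, 44 to 59 clustered is significantly above 34% and not different from 49.4%.

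**6. What a paired comparison gives.** Score the same 100 index cases without and with partner sequences. An assumed rise from 34 to 49 is a gain of 15 points, exact 95% interval 8.6 to 23.5. A rise from 40 to 50 is 10 points, 4.9 to 17.6. These intervals treat index men as independent, which they are not: two index men linked through one traced partner gain together. In the normal approximation, 15 points has half-width 1.96 × √(0.15 × 0.85/100) = 7.0 points. An assumed design effect of 2 makes it 7.0 × √2 = 9.9.

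**7. Why a p-value adds little.** Adding sequences mostly adds links. A link could be lost only if the re-estimated tree changes. If all changes run one way, six changed index cases already give an exact McNemar p of 2 × 0.5⁶ = 0.031.

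**The case against.** The strongest reply is that this is a side comparison. It sits among summary statistics, is worded as an additional comparison, gives the two percentages as examples, and carries no test or decision rule. Partner services also have their own place in the plan. Secondary objective 5 compares tracing and notification with outreach on partner testing, and secondary endpoint 5 counts men who name a partner and partners contacted and tested. That stands, and it limits the weight of the point. A reader might infer that the plan will formally test partner services against the literature, with false verdicts as frequent as in step 5, or that this is the study's only evaluation of partner services. The documents support neither.

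It does not remove the point. The sentence names the impact of partner services on cluster finding as its purpose. Endpoint 5 stops at naming, contact and testing. McNemar's test compares two ways of assigning cluster membership; neither shows how many more index cases cluster because partners were traced.

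A second reply is that the internal comparator is imperfect. This also stands. Being the partner of a newly diagnosed person is a Step 1 entry route (section 5.1.2, item 6b), so the tree without partners can still hold people found through partner services. The gain is near non-negative by construction, and resampling index men as if independent would ignore clustering. These are conditions on the remedy.

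A reader might also infer that reference 162 is misquoted, because section 3.5.3 says "In Montreal more than half the patients with newly diagnosed early HIV-1 infection are infected with viral variants that can be linked" while 11.5.2 gives 49.4%. The two may describe different subsets, and the documents cannot settle it. It is a minor editorial check.

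**Conclusion.** The point holds as a cheap improvement to a descriptive analysis. The comparison cannot separate partner services from setting, sampling, linkage rule and denominator, and its direction can depend on which of two figures 15.4 points apart is used. That conclusion rests on the plan's own text and needs no assumed rate. The illustrative gains, gaps and error rates do rest on assumed values of c, p, r, sample size and significance level, and show only that the distortion can be as large as a plausible true gain.

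The randomized viral load comparison is untouched. Nor should the paired gain be read as a causal effect of partner services: it is the added yield of traced partners' sequences among men who accept tracing.

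**What to change.** In the second analysis of section 11.5.2, replace the literature comparison as the measure of partner services with the following:

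- **Population.** Acute index cases at least; recent infections only if their sequencing is funded.
- **Held constant.** The same index men in the denominator, the same background sequences and the same linkage rule in both trees.
- **Report.** The percentage of index cases clustered without traced partners, the percentage with them, and the paired gain with a 95% interval that allows for dependence within clusters, for example by resampling clusters or connected components. Give no p-value.
- **Sensitivity analysis.** Flag participants who entered Step 1 as partners of a newly diagnosed case, and repeat the analysis counting them as traced partners.
- **Interpretation.** State that the gain is added yield among men who accept tracing, and is near non-negative by construction.

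Keep 49.4% and 34% as descriptive context, and check whether sections 3.5.3 and 11.5.2 report the same quantity from reference 162.

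The cost is SAP wording and a small amount of extra analysis. For the acute index cases no new samples or sequencing are needed, since their sequences and their contacts' are already planned and trees with and without partners are already named in the section.

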#### **11.5.3 The Impact of Immediate and Early (6 Months after Diagnosis) Antiretroviral Therapy on the Decay Dynamics of HIV Viral Load**

For men with acute/recent infection plasma VL will be measured at 0, 1, 2, 4, 6, 8, 12, 16, 24, 36 and 48 weeks. Semen specimens and rectal secretions will be collected from all men with acute/recent infection at 0, 1, 2, 4, 6, 8, 12, 16, 24, 36 and 48 weeks and stored. Semen HIV VL will be measured in these samples from 60 (30 acute/30 recent) ART-treated men and 60 (30 acute/30 recent) untreated men using established procedures in the University of Washington Virology Laboratory [177, 178]. This sample size is adequate to detect a 1.0-1.5  $\log_{10}$  change in VL associated with ART based on the following: semen viral load peaks about 30 days after infection, with mean 4.5 and standard deviation 1.6 ( $\log_{10}$  copies/ml) [185]. We compute the power of a two-sample t-test comparing two arms (ART vs. no ART) to detect significant difference with type I error 5%. With 30/group we have 66% power to detect a 1.0  $\log_{10}$  change and 94% power to detect a 1.5  $\log_{10}$  change based on a single viral load measure at peak per subject. The power would be greater if we use any summary measure of individual's multiple viral loads, e.g., mean across different time points.) We will seek separate funding to analyze additional samples, including rectal secretions. VL in semen and rectal secretions will be more informative for modeling the potential impact of ART on infectivity during this period than plasma VL as these 3 measures are only modestly related [177, 178].

The viral load trajectory will be plotted for each subject and for plasma, semen and rectal secretions separately. The mean trajectory and its confidence interval will be computed stratified by randomized arm and by acute or recent infection. The first-order rate of decay, the area under the curve, the peak viral load, and the lowest viral load will be computed for each subject and compared across arms. Multiple testing adjustment will be applied to control type I error.

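### McNemar's test is planned to assess agreement between traced and phylogenetic clusters, but it tests only whether the two proportions are equal, and no concordance measure is planned

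*Combined protocol and SAP*

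**What the plan says.** The second step of Section 11.5.2 sets out three things:

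- Description of the tree: "summary statistics on the inferred phylogenetic tree will be computed, including the number of clusters identified", with cluster sizes, the share of participants in clusters and the maximum window periods.
- An external comparison of that share: "we will also compare the percentage of MSM and transgender women in the cluster to that percentage seen in the literature using other approaches". The values cited are 49.4% and 34%.
- A comparison of the two ways of placing a person in a cluster: "McNemar's test will be conducted to evaluate the agreement between being in the clusters based on partner tracing", with phylogeny as the second method.

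The remaining tests in the section serve other purposes. For outcomes measured once, "we will use Chi-squared tests, Fisher's exact tests or Mann-Whitney U tests, as appropriate", and generalized estimating equations are named for longitudinal outcomes. These compare clustered with non-clustered participants. A further step compares acute with recent infection. Neither Section 11.5.2 nor the rest of Section 11 plans a measure of concordance between tracing and phylogeny. No alpha, power or effect size is given for the McNemar analysis; the 5% type I error in Section 11.5.3 belongs to the semen viral-load t-test.

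**The concern.** The stated purpose is agreement: does a person placed in a cluster by partner tracing also fall in a cluster by phylogeny? McNemar's test answers a different question, namely whether the two methods place the same proportion of people in clusters. People on whom the methods agree do not enter the test.

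A significant result does show one form of disagreement, because one method clusters more people than the other. A non-significant result is the difficulty. Under the stated purpose it could be reported as agreement even if the two methods select largely different people.

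The question is worth answering properly. The second primary objective (Section 11.1.1) relies on clusters identified by both routes, and Section 11.5.4 draws sexual-network data from both.

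**Working it through.** **Inputs.** The plan gives no figure to reproduce for this analysis, so the check rests on the test's definition and on illustrative tables.

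- N = 100, from Section 11.3: "Our initial sequencing efforts will focus on the 100 acutely infected men" (75 enrolled plus 25 not enrolled). Partners would add to this number.
- A clustering proportion of 34%, one of the two literature values cited in Section 11.5.2.
- A two-sided 5% level (assumed).
- All cell counts (assumed).

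**Formulas.** Let a = in a cluster by both methods, b = by tracing only, c = by phylogeny only, d = by neither, and n = a + b + c + d.

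- Exact McNemar p: two-sided binomial probability of the split b versus c, given b + c discordant people, each side having probability 1/2. When b + c = 0, p is set to 1.00 by convention.
- Observed agreement: Po = (a + d)/n.
- Chance agreement: Pe = [(a + b)(a + c) + (c + d)(b + d)]/n².
- Cohen's kappa = (Po - Pe)/(1 - Pe), with a large-sample 95% CI that treats people as independent.
- Positive agreement = 2a/(2a + b + c); negative agreement = 2d/(2d + b + c).

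Neither a nor d appears in the McNemar calculation. Whenever b = c, p = 1.00 whatever the agreement.

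**Set 1: both margins 34%.** Here Pe = 0.34² + 0.66² = 0.5512.

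| a/b/c/d | Po | Kappa (95% CI) | Exact McNemar p |
|---|---|---|---|
| 34/0/0/66 | 1.00 | 1.00 | 1.00 |
| 12/22/22/44 | 0.56 | 0.02 (-0.18 to 0.22) | 1.00 |
| 0/34/34/32 | 0.32 | -0.52 (-0.62 to -0.41) | 1.00 |

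Second row: kappa = (0.56 - 0.5512)/(1 - 0.5512) = 0.0088/0.4488 = 0.02; positive agreement = 24/68 = 0.35; negative agreement = 88/132 = 0.67.

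Third row: kappa = (0.32 - 0.5512)/0.4488 = -0.52; positive agreement = 0; negative agreement = 64/132 = 0.48.

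**Set 2: observed agreement 94%, tracing margin 34%, six discordant people.**

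| a/b/c/d | Phylogeny margin | Kappa (95% CI) | Exact McNemar p |
|---|---|---|---|
| 34/0/6/60 | 40% | 0.87 (0.77 to 0.97) | 2 × 1/64 = 0.031 |
| 33/1/5/61 | 38% | 0.87 (0.77 to 0.97) | 2 × 7/64 = 0.22 |
| 32/2/4/62 | 36% | 0.87 (0.77 to 0.97) | 2 × 22/64 = 0.69 |
| 31/3/3/63 | 34% | 0.87 (0.76 to 0.97) | 1.00 |

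First row: Pe = (34 × 40 + 66 × 60)/10,000 = 0.532, so kappa = (0.94 - 0.532)/(1 - 0.532) = 0.87.

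**Reading.** In Set 1 agreement ranges from perfect to worse than chance and p does not move. In Set 2 agreement is fixed and p moves from 0.031 to 1.00. It falls below 0.05 only when all six discordant people lie on one side, and there it correctly reports unequal margins. The p-value follows the split of the discordant people, not the level of agreement.

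**The case against.** The strongest reply is that one word is loose and the test is right. The McNemar sentence follows directly on a comparison of percentages in clusters, made to judge what partner services contribute. Whether tracing and phylogeny cluster different proportions of the same people is a natural question there, and McNemar's test answers it. This does not remove the point: the sentence names agreement between two memberships, which reads most naturally as person by person, and on the other reading the wording still needs correcting.

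A second reply is that the harm is conditional. The plan nowhere says that a non-significant result will be called agreement, and the test requires the very 2x2 table from which observed agreement follows. That is true, but the plan does not commit to reporting the table.

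Third, the illustration is partly extreme. Under Section 11.5.1 the tree is built from acutely infected index cases and their HIV-positive recent contacts, so a table with nobody clustered by both methods is hard to reconcile with the design. That row should be read as a theoretical limit. The 12/22/22/44 row makes the same point without it. Section 11.3 also plans 400 samples in all, so N may be larger; the behaviour of the test when b = c does not depend on N.

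The same design feature limits any agreement measure: because traced partners feed the tree, the two classifications are not ascertained independently. That caveat stands and belongs in the report.

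**Conclusion.** The concern holds. The named test cannot answer its stated question, and nothing else in Section 11 does. That conclusion follows from the definition of McNemar's test and does not rest on the assumed cell counts, which only show how far p and agreement can diverge.

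The impact is modest. It touches one descriptive analysis. The randomised viral-load comparison in Section 11.5.3, the substance-use comparison in Section 11.5.2 (which uses phylogenetic clusters only) and the model in Section 11.5.4 do not use the result. It should still be corrected, because the remedy costs little and the present wording invites a wrong reading of a non-significant test.

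**What to change.** Amend the McNemar sentence in Section 11.5.2 to:

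- report the 2x2 table of tracing-based by phylogeny-based cluster membership, with observed agreement (or positive and negative agreement) and Cohen's kappa, each with a 95% CI, as the agreement analysis;
- keep McNemar's test only for whether the two methods place different proportions of people in clusters.

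Add three cautions. Intervals that assume independent people are likely too narrow, because participants are linked. Agreement on in/out status does not show that both methods link the same pairs. Agreement will partly reflect who was traced and sequenced.

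If only the proportions were ever of interest, rewording the stated purpose would make the sentence correct, but the person-level question would remain unanswered.

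The cost is one or two sentences of text, a short note on the cautions and a little more analysis of the same paired data, with no new collection.

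### The substance-use cluster analysis pools index cases with their own partners but names only tests that assume independent persons, so its p-values are not valid and are probably too small

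*Combined protocol and SAP*

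**What the plan says.** Section 11.5.2 compares sexual behaviour and alcohol or drug use between persons who are and are not clustered by phylogeny. On the population it states: "Our analysis of the impact of substance use on clustered transmission will include all MSM and transgender women with acute/recent infection and their partners". On method, when an outcome is taken once per person, "we will use Chi-squared tests, Fisher's exact tests or Mann-Whitney U tests, as appropriate". The only allowance for dependence concerns the same person measured over time: "we will use the generalized estimating equation approach to account for correlations among repeated measures".

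The same paragraph plans the comparison twice, "using 2 set of trees: MSM and transgender women with acute/recent infection with or without partners", without saying which version is primary. It gives expected exposure for acutely infected index cases only: about 5% for cocaine and about 25% for AUD.

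Section 11.5.1 defines a link by two conditions: that "pair derived HIV-1 env sequences from two or more individuals form monophyletic clusters", and that the pairwise genetic distance carries a Bayesian posterior probability above 50%. Section 11.3 says the first sequencing effort covers "100 acutely infected men (75 enrolled plus 25 non-enrolled in immediate/deferred ART study") and their HIV-positive partners, 400 samples in all.

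Neither 11.5.1 nor 11.5.2 names a method for correlation between an index case and his partners, or between members of one cluster. No alpha, power or intraclass correlation is given for this comparison.

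**The concern.** Both variables in the two-by-two table can be correlated within a partner set. A person cannot be clustered alone: when a partner links to his index case, both become clustered. Partners enter the sample because they are partners, and people who have sex together may also drink or use drugs together. When exposure and cluster status are both positively correlated within sets, a test that counts every person as a separate observation understates the variance.

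GEE as planned does not help. It handles several measurements on one person, not several persons in one set.

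At stake is the comparison that speaks most directly to primary objective 2 (Section 11.1.1), the role of substance use in transmission clusters. An apparent enrichment of AUD or cocaine use in clusters would come with a p-value whose error rate is unknown.

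**Working it through.** The plan states no sample size or power for this comparison, so there is no figure of its own to reproduce.

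**Inputs from the documents**
- Index cases first sequenced: 75 + 25 = 100 (Section 11.3).
- Samples: 400 (Section 11.3). At one sample per person this implies 400 - 100 = 300 partners, or 400/100 = 4 persons per set on average.
- Exposure in index cases with acute infection: AUD about 25%, cocaine about 5% (Section 11.5.2).

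**Assumed, not in the documents**
- One sample per person, equal set sizes, and the same exposure in partners as in index cases.
- A nominal two-sided 5% test.
- Exposure ICC 0.1-0.3 and cluster-status ICC 0.3-0.8.

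**Formula.** With set size m, the design effect is DE = 1 + (m - 1) × ICC(exposure) × ICC(status). The true size of the nominal 5% test is 2 × [1 - Φ(1.96/√DE)].

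Example, m = 4, ICCs 0.2 and 0.8: DE = 1 + 3 × 0.2 × 0.8 = 1.48; 1.96/√1.48 = 1.611; size = 10.7%.

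| Exposure ICC | m = 4, status ICC 0.3 to 0.8 | m = 2, status ICC 0.3 to 0.8 |
|---|---|---|
| 0.1 | DE 1.09-1.24, size 6.0-7.8% | DE 1.03-1.08, size 5.3-5.9% |
| 0.2 | DE 1.18-1.48, size 7.1-10.7% | DE 1.06-1.16, size 5.7-6.9% |
| 0.3 | DE 1.27-1.72, size 8.2-13.5% | DE 1.09-1.24, size 6.0-7.8% |

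At m = 4, 400 persons carry the information of 400/1.72 = 233 to 400/1.09 = 367 independent persons. If the exposure ICC is zero, DE = 1 and the size is 5%.

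**Check by simulation under the null** (100 sets of 4, 3,000 runs per setting, exposure ICC 0.1/0.2/0.3). Status is partly shared: half the sets have no clustered member; in the rest the index case and one partner are clustered, and each other partner is clustered with probability 0.5.
- AUD 25%, chi-squared: 6.3% / 8.7% / 10.6%. The formula at status ICC 0.5 gives 6.8% / 8.6% / 10.4%.
- Cocaine 5%, Fisher's exact: 3.8% / 5.4% / 7.3%.
- AUD 25%, Fisher's exact: 4.7% / 7.0% / 8.7%.

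**The opposite direction.** Suppose every index case links to exactly one of three partners. Each set then has two clustered and two unclustered members, so the status ICC is -1/(m - 1) = -1/3 and DE = 1 - ICC(exposure) = 0.9 / 0.8 / 0.7. The size falls to 3.9% / 2.8% / 1.9% (simulated, chi-squared, AUD: 3.9% / 2.7% / 2.2%).

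That pattern is special. If instead each of three partners links to the index case independently with a probability between 0.2 and 0.6 (assumed), the status ICC stays positive at 0.06-0.23. At exposure ICC 0.2 the size is then 5.4-6.6%.

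**The case against.** A reader might infer that the p-values are certainly too small. The documents do not support that. It needs positively correlated substance use within sets and cluster status that tends to be shared, and the plan quantifies neither. Linkage is assigned pair by pair, so an index case may link to one HIV-positive partner and not to the others. The last calculation shows that the error can then run the other way. This stands, and it limits the claim to probable inflation.

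The sets may be smaller than 4. Section 11.3 expects that some men will not consent to partner tracing, and under Section 11.5.4 data come only from partners who consent. This stands too: with sets of 2 the inflation is modest. For cocaine, the conservatism of Fisher's exact test absorbs part of the inflation, and all of it at the lowest correlation with partly shared status.

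The plan already builds trees without partners, which removes index-partner pairs from that comparison. This is a partial answer only. The sentence on substance use says partners are included, neither version is named primary, and index cases can still link to each other.

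It may also seem that analysing index cases alone would settle the matter. It would not remove links between index cases, and it cuts about 400 persons to about 100, with about 5 cocaine users (5% of 100). That is fewer than the 233-367 effective persons left after allowing for dependence.

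Finally, objective 2 is worded as examining and modelling, and no alpha or decision rule is attached to this comparison. It should not be described as a formal confirmatory test that the plan gets wrong.

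**Conclusion.** The concern holds in limited form. The plan does more than omit a detail: for the pooled population it names specific methods that do not fit the data structure defined in Section 11.5.1. Following them gives p-values without a valid error rate, probably too small.

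The likely size is moderate: about 6-14% in place of 5% for a chi-squared test with sets of 4, and about 5-8% with sets of 2. All of this rests on assumed correlations, equal sets and one sample per person. Sizes below 5% are possible if index cases are clustered while most of their partners are not. The documents do not support a claim that a false finding of enrichment is to be expected. They do support changing the method before the analysis is run.

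**What to change.** Amend Section 11.5.2 so that any comparison that includes partners keeps the pooled population but replaces the independence tests with one of the following:
- GEE or a robust variance estimate with the group as the unit; or
- permutation or resampling of whole groups.

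Define a group as the connected set of persons joined by partner tracing or by phylogenetic linkage. Grouping by index-partner set alone is not enough, because clusters can span several sets when index cases link to each other.

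Report the already planned comparison without partners alongside, as a sensitivity analysis, with the same grouping for index cases that link to each other. State which comparison is primary, and report the observed group sizes and within-group correlations.

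No new data are needed. The cost is a little more analysis work and somewhat wider intervals: over the assumed range at m = 4, standard errors grow by a factor of √1.09 = 1.04 to √1.72 = 1.31 relative to the uncorrected analysis.
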